9.7.1.8.1 EXTENT OF EXPOSURE

The extent of exposure to study drug will be summarized as cumulative extent of exposure in 3-month intervals. The number and percent of subjects will be presented by treatment group.

Duration of exposure will be summarized using descriptive statistics in 3-month intervals. The number and percent of subjects will be presented by treatment group.

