9.7.1.8.2 ADVERSE EVENTS

The AE verbatim descriptions (investigator terms from the eCRF) will be classified into standardized medical terminology using the Medical Dictionary for Regulatory Activities (MedDRA). Adverse events will be coded to the MedDRA (Version 17.0 or higher) lower level term closest to the verbatim term. The linked MedDRA preferred term and primary system organ class (SOC) are also captured in the database.

A TEAE is defined as an AE that emerges during treatment, having been absent at pretreatment (Baseline) or

- Reemerges during treatment, having been present at pretreatment (Baseline) but stopped before treatment, or
- Worsens in severity during treatment relative to the pretreatment state, when the AE is continuous.

Only those AEs that are treatment-emergent will be included in summary tables. All AEs, treatment-emergent or otherwise, will be presented in subject data listings.

The TEAEs will be summarized by treatment group on the Safety Analysis Set. The incidence of TEAEs will be reported as the number (percentage) of subjects with TEAEs by SOC and preferred term. A subject will be counted only once within an SOC and preferred term, even if the subject experienced more than 1 TEAE within a specific SOC and preferred term. The number (percentage) of subjects with TEAEs will also be summarized by maximum severity (mild, moderate, or severe). The number (percentage) of subjects with TEAEs will also be summarized by relationship to study drug (Yes [related] and No [not related]).

The number (percentage) of subjects with treatment-related TEAEs will be summarized by SOC and preferred term. Treatment-related TEAEs include those events considered by the investigator to be related to study drug. The number (percentage) of subjects with treatment-related TEAEs will also be summarized by maximum severity (mild, moderate, or severe).

Adverse events will be summarized by the following subgroups: *ApoE4* status (positive or negative), prior treatment with AChEIs or memantine (no or yes), and clinical subpopulation (MCI/Prodromal or mild AD).

The number (percentage) of subjects with TEAEs leading to death will be summarized by MedDRA SOC and preferred term for each treatment group. A subject data listing of all AEs leading to death will be provided.

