9.7.3 Interim Analysis

The MCI/Prodromal Cohort

The Bayesian interim analyses and response adaptive randomization will be conducted by an unblinded external independent analysis group in accordance with the protocol. Oversight of the Bayesian interim analyses and response adaptive randomization will be conducted by an independent unblinded committee that has expertise with Bayesian adaptive design in clinical studies to ensure that the response adaptive randomization process and interim analyses perform as expected. The analysis group will provide the interim analysis outcomes to the committee at each interim analysis. The committee will ensure the integrity of the interim analysis and response adaptive randomization process through review of efficacy data. In addition, the committee will act in an independent advisory capacity to monitor the Bayesian interim analysis outcomes according to the early success and futility boundaries prespecified in the protocol. The committee will not be charged with any subject safety issues; this will remain the responsibility of the DSMB.

If the predefined early success criteria are met during the recruitment period, further recruitment and enrollment of MCI/Prodromal subjects into the study will stop (following confirmation from the Sponsor's Senior Management) and all currently randomized subjects will complete the full 18 months of treatment. No further interim analyses will be conducted after achieving early success.

If the predefined threshold for futility is reached, no additional subjects will be randomized into the study and the treatment of subjects already randomized into the study will stop and the study will be declared as "failed". All subjects will be monitored for safety for 3 months following their last dose.

If neither early success nor futility is reached and the study reaches full randomization, all subjects will complete 18 months of treatment. Interim efficacy analyses will be conducted every 3 months after full randomization is reached to assess futility and early success until all subjects complete 18 months of treatment. After full randomization, all study subjects will stop treatment only in the event of futility.

The DSMB will continue to monitor the safety aspects of the study throughout Stage A and Stage B. Details will be provided in the DSMB Charter. The study may be stopped for safety at any time.

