9.7.4 Other Statistical/Analytical Issues

Adaptive Randomization in the MCI/Prodromal Cohort

Randomization to placebo or 1 of 3 dose groups of E2609 will be fixed for the first 100 subjects randomized in the study (1:1:1:1; placebo to each of the 3 active doses). Randomization probabilities to each treatment group will be updated at each interim analysis, such that the randomization probability will be increased for the placebo group and dosage groups that represent the potential target dose (ED₉₀), and simultaneously decreased for other active arms.

Within the 2 clinical populations (MCI/Prodromal and mild AD), subjects will be stratified at randomization by *ApoE4* status (positive or negative) and prior treatment with AChEIs or memantine or both (yes or no).

Subjects with mild AD will be randomized to placebo or 1 of 2 dose groups of E2609.

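### If futility stops treatment during or soon after recruitment of the MCI/Prodromal cohort, crude TEAE percentages can show dose differences that come only from unequal exposure

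*Protocol*

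**What the plan says.** Section 9.7.1.8.2 sets the grouping, "The TEAEs will be summarized by treatment group on the Safety Analysis Set", and the measure, "The incidence of TEAEs will be reported as the number (percentage) of subjects with TEAEs by SOC and preferred term". Each subject counts once per term. Treatment-related TEAEs, deaths, SAEs and TEAEs leading to discontinuation are handled the same way. An event qualifies only if it begins, returns or worsens during treatment. No exposure-adjusted or time-to-event summary of adverse events is stated.

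Section 9.7.1.8.1 reports exposure by arm in a separate table: "Duration of exposure will be summarized using descriptive statistics in 3-month intervals".

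Section 9.7.4 describes allocation in the MCI/Prodromal cohort. It "will be fixed for the first 100 subjects randomized in the study (1:1:1:1; placebo to each of the 3 active doses"), and afterwards "the randomization probability will be increased for the placebo group and dosage groups that represent the potential target dose", with the shares of the remaining doses cut in step. The probabilities are not given.

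Section 9.7.3 checks futility at every interim from 100 randomized, every 50 subjects up to 500, then every 3 months. If the boundary is crossed, "no additional subjects will be randomized into the study and the treatment of subjects already randomized into the study will stop". Section 9.7.1.6 calls the boundary binding. After early success, or if neither boundary is crossed, all randomized subjects complete 18 months.

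**The concern.** A percentage of subjects compares arms fairly when they are observed for similar lengths of time. Here the allocation rule links arm to entry date, and the futility rule cuts later entrants short. A dose that the algorithm moved away from keeps a high proportion of its subjects from the first 100, who have been on drug longest. Placebo and the favoured dose hold mostly recent entrants.

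Safety and tolerability is a primary objective (section 8.1), and sections 7.1 and 9.2.6 single out infection, herpes and rash. After a futility stop, safety by dose is one of the main results left to report. An artefact of allocation could then create or hide a dose relation. This is more than a detail left to the SAP, because the protocol states a measure that its own allocation and stopping rules can distort.

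**Working it through.** The protocol states no figure on this point, so there is nothing to reproduce. The question is how far apart the percentages can be when the hazard is identical in every arm.

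**From the protocol.** 60 subjects in Stage A and up to 440 in Stage B; 1:1:1:1 for the first 100; 18 months of treatment; at most 40 months for Stage B (synopsis).

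**Assumed.**
- Stage A enters evenly over 9 months, followed by a 4.5-month gap, so Stage B opens at month 13.5.
- Stage B accrual: 40 − 18 − 3 = 19 months for 440 subjects, 440/19 ≈ 23 per month (range 15 to 30).
- Shares after subject 100 (placebo/5/15/50 mg): strong skew 40/5/10/45%, mild skew 35/15/20/30%.
- The same constant hazard in all arms, 30% over 18 months: λ = −ln(0.70)/18 = 0.0198 per month.

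**Formulas.** Exposure x = min(18, stop date − entry date). Arm size = 25 + share × (n − 100). Crude incidence = mean of 1 − exp(−λx) over the arm.

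**Stop at 300 randomized, 23 per month.** The stop falls at 13.5 + 240/23 = 23.9 months.

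| | Placebo | 5 mg | 15 mg | 50 mg | Max/min exposure |
|---|---|---|---|---|---|
| Strong skew: n | 105 | 35 | 45 | 115 | |
| mean months | 6.7 | 11.5 | 9.9 | 6.5 | 1.76 |
| % with event | 12.0 | 19.8 | 17.2 | 11.7 | |
| Mild skew: n | 95 | 55 | 65 | 85 | |
| mean months | 7.0 | 8.9 | 8.2 | 7.3 | 1.27 |
| % with event | 12.4 | 15.5 | 14.4 | 12.9 | |

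Under strong skew the first 100 supply 25/35 = 71% of the 5 mg arm but 25/115 = 22% of the 50 mg arm.

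**Exposure ratio by timing of the stop** (15 to 30 per month):
- 200 to 400 randomized: 1.34 to 1.87 (strong), 1.12 to 1.34 (mild)
- 500 randomized: 1.07 to 1.54 over both skews
- 6 months after full randomization: 1.02 to 1.18
- 12 months after: 1.01 to 1.04
- no futility stop: 1.00

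**Second calendar.** Stage B opens at month 14 with 26 per month; hazard 2% per month. For a stop at 400, a 5% share gives 12.0 months and 20.8% with the event, against 7.5 months and 13.5% for a 40% share: 20.8/13.5 = 1.54. A 10% share gives 18.0%, and 18.0/13.5 = 1.33.

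**Split not fixed by hand.** A simplified simulation of the adaptive rule (300 runs per setting; effect, SD and accrual assumed) gives, among trials stopped for futility, a median exposure ratio of 1.18 to 1.43 across settings. The 10th percentile is 1.01 to 1.06 and the 90th is 1.58 to 2.01. The median spurious spread is about 3 to 6 percentage points for the 30% event. The ratio exceeds 1.25 in about 35 to 70% of futility stops.

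**Would person-time rates alone solve it?** Under constant hazard, yes: 0.0198 × 1200 = 23.8 per 100 person-years in every arm. For early-onset events, no. On the second calendar (stop at 400), with a hazard of 0.10 in month 1 only and equal in all arms, the crude percentages are 9.4% and 9.2%, nearly correct, but the person-time rate ratio (5% share to 40% share) is about 0.64. A time-to-first-event estimate handles both cases. The 6-month risk is 1 − exp(−0.0198 × 6) = 11.2% in every arm in the first case, and 1 − exp(−0.10) = 9.5% in every arm in the second.

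**The case against.** The strongest reply is that this happens in one branch of the design only. It needs a futility stop, and a fairly early one. That is right, and it limits the point. A reader might infer that adaptive allocation distorts the safety percentages in general. The protocol does not support that: all randomized subjects are to complete 18 months after early success or if no boundary is crossed, and the mild AD cohort keeps a fixed 1:1:1 schedule.

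A reader might also infer that exposures must be very different, or that the down-weighted arms consist mainly of subjects near 18 months. Neither follows. The shares are unpublished, and mild skew gives ratios of only 1.1 to 1.3. On the second calendar (stop at 400, 5% share), 37.5% of the arm has at least 16 months and the mean is 12.0 months.

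The artefact can also be no larger than sampling noise. In that same case, with 40 and 145 subjects, the gap is 20.8 − 13.5 = 7.3 points and its standard error is √(0.208 × 0.792/40 + 0.135 × 0.865/145) = 7.0 points. Safety is analysed descriptively and the exposure table would reveal the imbalance. This tempers the importance, but the displacement is systematic across all event terms, and a separate exposure table does not correct the percentages.

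Finally, the SAP may add suitable summaries. It may, and nothing in section 9.7.1.8.2 forbids them. The protocol as written still fixes only the crude measure.

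**Conclusion.** The point holds conditionally. In the MCI/Prodromal cohort, a futility stop during or soon after recruitment can leave down-weighted doses with mean exposure about 1.1 to 1.3 times that of the shortest-exposed arm under mild skew, and up to about 1.9 times under strong skew. For an event with 30% incidence at 18 months, the worked example shows 19.8% against 11.7% of subjects (strong) or 15.5% against 12.4% (mild) with no true difference. The effect is small 6 months after full randomization and close to nil at 12 months.

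These sizes rest on assumed accrual, shares and a constant common hazard. The direction rests only on the protocol's allocation and stopping rules. Making person-time rates the sole between-arm comparison is not supported either: section 7.1 describes lymphocyte reductions by Day 8 and Day 15, and section 9.4.4 reports herpes relapses and rash in a 14-day dosing study. For such early-onset events, rates could mislead in the opposite direction.

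**What to change.** In section 9.7.1.8.2, keep the number and percentage of subjects. Add that, if treatment is stopped early for all subjects, time to first event will also be reported by arm (Kaplan-Meier or cumulative incidence) at fixed times such as 3, 6 and 12 months, censored at the end of the TEAE window. Apply it to TEAEs overall, SAEs, TEAEs leading to discontinuation, and infections, herpes and rash. Give exposure-adjusted rates as a supplement, not as the only between-arm comparison.

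The cost is a sentence or two and a few tables from data already collected. Late estimates will be imprecise in small arms. The method also assumes that risk at a given time on drug does not depend on entry date, which deserves a note because Stage A is run in the United States only and Stage B globally.

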9.7.1.8.3 LABORATORY VALUES

Laboratory results will be summarized using International System of Units, as appropriate. For all quantitative parameters listed in [Section 9.5.1.5.3](#), the actual value and the change from baseline to each postbaseline visit and to the end of treatment (defined as the last on-treatment value) will be summarized by visit and treatment group using descriptive statistics. Qualitative parameters listed in [Section 9.5.1.5.3](#) will be summarized using frequencies (number and percentage of subjects), and changes from baseline to each postbaseline visit and to end of treatment will be reported using shift tables. Percentages will be based on the number of subjects with both nonmissing baseline and relevant postbaseline results.

Laboratory test results will be assigned a low/normal/high (LNH) classification according to whether the value was below (L), within (N), or above (H) the laboratory parameter's reference range. Within-treatment comparisons for each laboratory parameter will be based on 3-by-3 tables (shift tables) that compare the baseline LNH classification to the LNH classification at each postbaseline visit and at the end of treatment. Similar shift tables will also compare the baseline LNH classification to the LNH classification for the highest and lowest value during the treatment period.

[Appendix 1](#) (Sponsor's Grading for Laboratory Values) presents the criteria that will be used to identify subjects with treatment-emergent markedly abnormal laboratory values (TEMAVs). Except for phosphate, a TEMAV is defined as a postbaseline value with an increase from baseline to a Grade of 2 or higher. For phosphate, a TEMAV was defined as a postbaseline value with an increase from baseline to a Grade of 3 or higher. When displaying the incidence of TEMAVs, each subject may be counted once in the laboratory parameter high and in the laboratory parameter low categories, as applicable.

Lymphocyte subsets (ie, CD4 [T helper cells], CD8 [cytotoxic T cells], CD19 [B cells], CD16/CD56 [natural killer cells] and CD14 [macrophages]) and regulatory T cells will be summarized in the same manner as other laboratory parameters. Mean lymphocyte subsets and the mean change from baseline in lymphocyte subsets will also be displayed graphically over time by dose.

Serum IgG, IgM, and IgA will be measured and summarized in the same manner as other laboratory parameters.

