| Bilirubin (hyperbilirubinemia) | >1.2 – 1.5×1.2 | >1.5 – 3.0×1.2 | >3.0 – 10.0×1.2 | >10.0×1.2 |
| Calcium, serum-low (hypocalcemia) (conversion to mmol×0.25) | <8.5 – 8.0 mg/dL <2.13 – 2.0 mmol/L | <8.0 – 7.0 mg/dL <2.0 – 1.75 mmol/L | <7.0 – 6.0 mg/dL <1.75 – 1.5 mmol/L | <6.0 mg/dL <1.5 mmol/L |
| Calcium, serum-high (hypercalcemia) | >10.6 – 11.5 mg/dL >2.65 – 2.9 mmol/L | >11.5 – 12.5 mg/dL >2.9 – 3.1 mmol/L | >12.5 – 13.5 mg/dL >3.1 – 3.4 mmol/L | >13.5 mg/dL >3.4 mmol/L |
| Cholesterol, serum-high (hypercholesterolemia) (conversion to mmol/L ×0.02586) | 0 -19 years >169 – 300 mg/dL >4.37 – 7.75 mmol/L 19 -150 years >199 – 300 mg/dL >5.15 – 7.75 mmol/L | >300 – 400 mg/dL >7.75 – 10.34 mmol/L | >400 – 500 mg/dL >10.34 – 12.92 mmol/L | >500 mg/dL >12.92 mmol/L |
| Creatinine | Female >1.00 mg/dL – 1.5×1.00 Male >1.27 mg/dL – 1.5×1.27 | Female >1.5 – 3.0×1.00 Male >1.5 mg/dL – 3.0×1.27 | Female >3.0 – 6.0×1.00 Male >1.5 mg/dL – 3.0×1.27 | Female >6.0×1.00 Male >1.5 mg/dL-3.0×1.27 |
| Gamma glutamyl transpeptidase | Female >60 IU/L – 3.0×60 Male >65 IU/L – 3.0×65 | Female >3.0 – 5.0×60 Male >3.0 – 5.0×65 | Female >5.0 – 20.0×60 Male >5.0 – 20.0×65 | Female >20.0×60 Male >20.0×65 |
| Glucose, serum-high (hyperglycemia) (conversion to mmol/L ×0.0555) | Fasting glucose value >99 – 160 mg/dL >5.5 – 8.9 mmol/L | Fasting glucose value >160 – 250 mg/dL >8.9 – 13.9 mmol/L | >250 – 500 mg/dL; >13.9 – 27.8 mmol/L; hospitalization indicated | >500 mg/dL; >27.8 mmol/L; life-threatening consequences |
| Glucose, serum-low (hypoglycemia) | <65 – 55 mg/dL <3.6 – 3.0 mmol/L | <55 – 40 mg/dL <3.0 – 2.2 mmol/L | <40 – 30 mg/dL <2.2 – 1.7 mmol/L | <30 mg/dL <1.7 mmol/L life-threatening consequences; seizures |
| Phosphate, serum-low (hypophosphatemia) (conversion to mmol/L ×0.323) | <2.5 – 2.5 mg/dL <0.81 – 0.8 mmol/L | <2.5 – 2.0 mg/dL <0.8 – 0.6 mmol/L | <2.0 – 1.0 mg/dL <0.6 – 0.3 mmol/L | <1.0 mg/dL <0.3 mmol/L life-threatening consequences |
| Potassium, serum-high (hyperkalemia) | >5.5 – 5.5 mmol/L | >5.5 – 6.0 mmol/L | >6.0 – 7.0 mmol/L hospitalization indicated | >7.0 mmol/L life-threatening consequences |
| Potassium, serum-low (hypokalemia) | <3.5 mEq/L – 3.0 mmol/L | <LLN – 3.0 mmol/L; symptomatic; intervention indicated | <3.0 – 2.5 mmol/L hospitalization indicated | <2.5 mmol/L life-threatening consequences |

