| Sodium, serum-high (hypernatremia) | >144 mEq/L – 150 mmol/L | >150 – 155 mmol/L | >155 – 160 mmol/L hospitalization indicated | >160 mmol/L life-threatening consequences |
| Sodium, serum-low (hyponatremia) | <134 mEq/L – 130 mmol/L | Not applicable | <130 – 120 mmol/L | <120 mmol/L life-threatening consequences |
| Triglyceride, serum-high (hypertriglyceridemia) | 150 – 300 mg/dL 1.71 – 3.42 mmol/L | >300 – 500 mg/dL >3.42 – 5.7 mmol/L | >500 – 1000 mg/dL >5.7 – 11.4 mmol/L | >1000 mg/dL >11.4 mmol/L life-threatening consequences |
| Uric acid, serum-high (hyperuricemia) | Female >7.1 – 10 mg/dL Male >8.6 – 10 mg/dL Both ≤0.59 mmol/L without physiologic consequences | Not applicable | Female >7.1 – 10 mg/dL Male >8.6 – 10 mg/dL Both ≤0.59 mmol/L without physiologic consequences | >10 mg/dL >0.59 mmol/L life-threatening consequences |

LLN = lower limit of normal, ULN = upper limit of normal.

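### Four rows of the laboratory grading table behind the TEMAV definition carry wrong limits: lymphocytes, neutrophils, male creatinine and uric acid

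*Protocol*

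**What the plan says.** Section 9.7.1.8.3 of the protocol makes Appendix 1 the working criterion. The appendix "presents the criteria that will be used to identify subjects with treatment-emergent markedly abnormal laboratory values (TEMAVs"). The rule is: "a TEMAV is defined as a postbaseline value with an increase from baseline to a Grade of 2 or higher". For phosphate the threshold is Grade 3. The same section also classes every result against its reference range ("Laboratory test results will be assigned a low/normal/high (LNH) classification") and builds shift tables from that class.

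The Appendix 1 rows at issue are:

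- **Lymphocytes (×10⁹/L):** Grade 1 is below 0.70 down to 0.8; Grade 2 is below 0.8 down to 0.5.
- **Neutrophils (×10⁹/L):** Grade 1 is below 1.40 down to 1.5; Grade 2 is below 1.5 down to 1.0.
- **Creatinine:** Grade 1 for men is "Male >1.27 mg/dL – 1.5×1.27". The Grade 2 cell is "Female >1.5 – 3.0×1.00 Male >1.5 mg/dL – 3.0×1.27". The male entry "Male >1.5 mg/dL – 3.0×1.27" then stands again under Grade 3 and, apart from spacing, under Grade 4, while the female limits move up to 3.0–6.0 and then above 6.0.
- **Uric acid:** Grades 1 and 3 both run from above 7.1 (women) or 8.6 (men) to 10 mg/dL, with the same qualifier, "Both ≤0.59 mmol/L without physiologic consequences". Grade 2 is marked not applicable, and Grade 4 is above 10 mg/dL.

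**The concern.** A grading scale has to give each result one grade, rising with severity, and should not put a normal result in the range called markedly abnormal. These rows fail in different ways. For the two blood counts, one section would report the same value as normal in one table and markedly abnormal in another. For male creatinine, the most extreme values drop out of the definition. For uric acid, a value just above normal sits in a grade that counts and in one that does not.

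Section 8.1 makes safety, including immunological and haematological parameters, a primary objective. A programmer who follows Appendix 1 as printed would have to improvise or would produce wrong counts.

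**Working it through.** **Inputs.** The limits come from Appendix 1 and the rule from Section 9.7.1.8.3. The cells label only the upper limit of normal. The lower limits of 0.70 and 1.40 are inferred from the Grade 1 bound, because the neighbouring rows are built that way (leukocytes below 3.40 to 3.0, platelets below 155 to 75). For low-type rows a value x has a grade if lower ≤ x < upper; for high-type rows, if lower < x ≤ upper. The protocol states no summary figure to reproduce here.

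**Blood counts.** Width of Grade 1 = upper bound − lower bound:

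- Leukocytes (control): 3.40 − 3.0 = 0.4
- Platelets (control): 155 − 75 = 80
- Lymphocytes: 0.70 − 0.8 = −0.1, empty
- Neutrophils: 1.40 − 1.5 = −0.1, empty

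Grade 2 starts 0.8 − 0.70 = 0.1 above the implied lower limit for lymphocytes, and 1.5 − 1.40 = 0.1 above it for neutrophils. Lymphocytes of 0.70, 0.75 and 0.79, and neutrophils of 1.40, 1.45 and 1.49, are all class N and Grade 2. A subject who reaches these values from an ungraded baseline becomes a TEMAV. A subject already in the band at baseline does not, because the grade must increase.

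**Male creatinine.** 1.5 × 1.27 = 1.905 and 3.0 × 1.27 = 3.81 mg/dL. Grades met on the literal text:

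| mg/dL | Men | Women |
|---|---|---|
| 1.3 | 1 | 1 |
| 1.6 | 1, 2, 3, 4 | 2 |
| 2.5 | 2, 3, 4 | 2 |
| 3.9 | none | 3 |
| 5 | none | 3 |
| 8 | none | 4 |

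**Uric acid.** A woman at 7.5 or 9 mg/dL, or a man at 9 mg/dL, meets Grades 1 and 3 together. Under Grade 1 this is not a TEMAV; under Grade 3 it is. At 10.5 mg/dL both sexes are Grade 4.

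**Size for lymphocytes.** The protocol gives no distribution, so these figures rest on an assumption: log-normal counts with median 1.7, or 1.36 after a 20% fall (1.7 × 0.8), and log-SD 0.25 to 0.35. With P(X < c) = Φ(ln(c/median)/log-SD), at log-SD 0.30:

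- Median 1.7: P(<0.70) = Φ(−2.96) = 0.0015; P(<0.80) = Φ(−2.51) = 0.0060. The band holds 0.0060 − 0.0015 = 0.0045 of values, and its share of those at Grade 2 or higher is 74%.
- Median 1.36: P(<0.70) = Φ(−2.21) = 0.0134; P(<0.80) = Φ(−1.77) = 0.0385. The band holds 0.0385 − 0.0134 = 0.0251, a share of 65%.

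Over log-SD 0.25 to 0.35 the band holds 0.1% (0.0013 − 0.0002, median 1.7, log-SD 0.25) to 3.6% (0.0648 − 0.0289, median 1.36, log-SD 0.35). The in-range share runs from 85% down to 55% between the same two corners.

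**Extraction check.** The file holds two copies of Appendix 1, and both carry these entries, so a PDF reading error is unlikely.

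**The case against.** The best case for leaving this alone is that little depends on it. The compound's lymphocyte signal, as Section 7.1 describes it, lies in CD4, CD8 and CD19 counts. Appendix 1 has no rows for these subsets, and they are followed against separate absolute thresholds and a fall of more than 33% in Section 9.3.3. Total lymphocytes and neutrophils also have change-from-baseline summaries and shift tables, including one for the lowest value on treatment. A male creatinine above 3.81 mg/dL still appears there as high. The same rule applies in every arm. All of this stands and limits the point.

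On creatinine, the female cell and the ALT, AST and GGT rows suggest that the leading 1.5 is a multiplier of the reference limit. On that reading male Grade 2 starts at 1.905 mg/dL and the overlap with Grade 1 disappears. The triple repetition and the missing grade above 3.81 mg/dL remain on either reading. Because a TEMAV is yes or no at Grade 2, the repetition affects TEMAV status only above 3.81 mg/dL.

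Two stronger readings are tempting. A reader might infer that the TEMAV table would fill with normal counts. The 55% to 85% is a share of a small tail, counted per value, under an assumed distribution and before the required increase from baseline, so it does not show this. A reader might also infer that monitoring of the immunological signal is compromised; the separate subset thresholds show that it is not.

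One qualification applies. The file contains two protocol texts. Where Section 9.5.1.5.1 covers events associated with special situations, the laboratory AE criteria do not use these grades. In the other text that section counts a worsening to Grade 2 or higher as an AE, so under that text the defect would also reach AE reporting.

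**Conclusion.** The point holds as a set of wrong thresholds in a table the protocol itself makes operative; it is not detail left to the SAP. As written, the rule flags some counts at or above the implied lower limit, misses male creatinine above 3.81 mg/dL, and leaves uric acid status between the upper limit of normal and 10 mg/dL undetermined.

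The consequence is limited to the TEMAV table. In absolute terms the lymphocyte band is small, and its size depends on the assumed medians and spread; the statement about in-range values depends on the inferred lower limits. No size is claimed for neutrophils or uric acid. The creatinine and uric acid defects are visible from the text alone. The correction should be made, but the point does not call the trial's safety monitoring into question.

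**What to change.** Before TEMAVs are tabulated:

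1. Reconcile the lymphocyte and neutrophil rows with the laboratory's reference ranges so that no in-range value is Grade 2. At minimum, require class L as well as Grade 2 for a TEMAV. That minimum stops normal values being counted, but it leaves Grade 1 empty and so does not fully repair the scale.
2. Write male creatinine with the female row's multipliers: Grade 2 above 1.5 to 3.0 × 1.27 (1.905 to 3.81 mg/dL), Grade 3 above 3.0 to 6.0 × 1.27 (3.81 to 7.62), Grade 4 above 6.0 × 1.27 (7.62).
3. Correct the uric acid Grade 3 cell so that it differs from Grade 1, and state that values in the Grade 1 range are not TEMAVs. The documents do not say what Grade 3 was meant to contain, so the sponsor has to supply it. Moving the uric acid threshold to Grade 4 would hide the faulty cell without repairing it.

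The cost is a correction to Appendix 1 and, if the class L condition is used, one sentence in Section 9.7.1.8.3. No data collection changes.
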